10.7 Treatment Compliance

The investigational product will be provided to patients by the Investigator, who will thus monitor compliance at each visit.

To monitor treatment compliance, patients will be asked to bring back the two bottles provided at the randomization visit (V2), including all unused tablets.

The investigational drug supplies, the unused returned investigational drug will be duly recorded in the drug accountability forms, as source documents, by the authorized study centre personnel and then reported in the e-CRFs. Any discrepancy must be clearly documented.

A level of compliance >80% during the treatment period will be considered satisfactory.

10.8 Prior and Concomitant Therapy

Prohibited Treatment

Initiation of beta-blocker treatment is not allowed from the screening visit (V1) to the end of followup (Day 60; V4) included. Patients already on chronic treatment with beta-blockers at the screening visit can be enrolled in the study.

Initiation of any oestroprogestinic or progestogen contraceptive or oestroprogestinic or progestogen replacement therapy is not allowed from V1 to V4 included. Patients already treated with oestroprogestinic or progestogen contraceptives or oestroprogestinic or progestogen replacement therapy before V1 can be enrolled in the study.

The following medication will not be permitted from V1 to V4 included:

- Biologic or non-biologic immunomodulatory or immunosuppressive drugs; warfarin (or other coumarins); niacin; topical facial or systemic antibiotic treatments; neomycin or any other low-absorbable oral antibiotics (such as marketed rifaximin); topical facial, inhaled or systemic corticosteroids; topical and systemic retinoids; any other topical or systemic treatment for rosacea (including also laser and pulsed light, etc.).
- Any cancer-related treatment.
- "Over the counter" formulations including intestinal and topical skin probiotics.

• Any other experimental treatment

Concomitant Permitted Treatments

All other medications for concomitant chronic conditions are allowed and should be maintained constant throughout the whole study.

11. STUDY PROCEDURES

11.1 Visit Schedule

Social Media recruitment path only

	Remote Data Recording	Central Reader	Phone contact for
	(via study website)	Validation	scheduling clinic visit
Visits	V0		
Days		Within 2 working	Within 1 week after C.
		days from V0	Reader validation
Online pre-screening consent	Х		
Contact details, demographics, health	Х		
related behaviour			
Medical and surgery history questionnaire	Х		
Concomitant medications questionnaire	Х		
Face images upload	Х		
Preliminary compliance with		Х	Х
inclusion/exclusion criteria			
Study description to the subject			Х
Decision recording			Х
Appointment set-up			Х

Social Media and On-site recruitment paths

	Screening	Baseline/	End of	End of	Early	Unscheduled
	Period	Randomization	Treatment	Study Visit	Termination	visit
		Visit	Visit		Visit	
	V1	V2	V3	V4	ETV	UV
Days	-30 to -1	1	30 (±1)	60 (±3)	From 1 to 60	From 1 to 60
Written informed consent	Х					
Demographics collection	Х					
and health-related						
behaviour assessment						
Relevant rosacea-	Х					
associated medical history						
Relevant non-rosacea-	Х					
associated medical history						
Previous and Concomitant	Х	Х	Х	Х	Х	Х
medications						
Adverse events collection	Х	Х	Х	Х	Х	Х
Vital signs (heart rate,	Х	Х	Х	Х	Х	Х
blood pressure, body						
temperature)						
Weight, Height* and BMI		Х	Х		Х	
Complete Physical	Х	Х	Х	Х	Х	Х
Examination						

Final Version 2.0 25 March 2022

Rosacea-associated facial	Х	Х	Х	Х	Х	X4
inflammatory lesion count						
(papules and pustules)						
Five-points Investigator's	Х	Х	Х	Х	х	X4
Global Assessment (IGA)						
of Rosacea Severity						
Evaluation of erythema,	Х	х	Х	х	Х	X4
telangiectasia, ocular						
manifestations and						
phymatous changes						
Visual Analogue Scale	Х	х	Х	х	Х	X ⁴
(VAS) for pain,						
burning/stinging and						
itching						
Abdominal symptoms						
questionnaire (IBS-SSS) ¹					-	
Dermatology Life Quality					`	
Index Questionnaire ¹						
Clinical chemistry,	Х		Х	х	Х	X ⁴
haematology, urinalysis						
Contraception		Х				
recommendations and/or						
adherence^						
Serum pregnancy test^	Х					
Urine pregnancy test^		Х	Х	Х	Х	X4
Lactulose Breath test	Х		Х		Х	X4
Inclusion/exclusion criteria	Х	Х				
Randomization		Х				
Blood sampling for PK		X ²	X ³			
analysis^^						
Overnight stay^^			Х			
Drug dispensing		Х				
Drug accountability			Х		Х	

^^ Only in subjects participating in the PK sub-study;

¹To be collected every 10 days, starting from V2 up to V4, and recording patient's responses through an electronic diary (ePRO).

²Sampling to be performed right before and after the first morning dose of Rifaximin-EIR at V2 (Day 1) at the following time points: immediately pre-dose and at 0.5, 1, 1.5, 2, 3, 4, 6, 8 hours post-dosing.

³Sampling to be performed right before and after the morning dose of Rifaximin-EIR on day 30 at the following time points: immediately pre-dose and at 0.5, 1, 1.5, 2, 3, 4, 6 and 8, 12, 22, 24, 30 hours post-dosing (single dose at Day 30). The sampling started at V3 (Day 30) and will end after overnight stay, as appropriate.

⁴If judged necessary by the Investigator

11.2 Study Evaluations/Procedures

Procedures for Social Media recruitment path

Specific advertisements targeted to rosacea subjects posted in selected social media will re-direct subjects interested in participating to a dedicated study website.

11.2.1. Remote data recording (visit V0)

In a dedicated study website, a *prospective participant* will be asked to:

- review a concise study description;
- provide online pre-screening consent;
- provide contact details;
- provide demographics (e.g. age, gender, ethnicity, educational level, profession, etc.);
- provide data on health-related behaviour (e.g. smoking, alcohol consumption);
- complete an online medical history and concomitant medication questionnaire;
- upload either three pictures of their face (one frontal and two lateral [right and left side] photos) or a short video of the face.

11.2.2 Central Reader Validation

This task will be performed no later than 2 working days after V0. A Central reader (*expert dermatologist*) will:

- check preliminary compliance with inclusion/exclusion criteria based on the
 - review of personal and clinical data (including medical history, concomitant medications etc.) posted on the website,
 - o review of patient's images downloaded on the website,
- address all the suitable pre-screened candidates to the closest investigational site for scheduling the remote screening. The Study Navigator may assist with referring the candidates to the closest investigational site after the central reader confirms the candidates' preliminary eligibility.

11.2.3 Phone Contact with the Subject

This task will be performed no later than 1 week after the candidate validation has been occurred. The investigational team will call the prospective participant and in case the subject accepts to move forward, a clinic visit will be scheduled. If the site considers also to perform the lactulose breath test (L-BT) at the clinic in this occasion, detailed patient's instruction on L-BT preparation will be provided. In case the subject does not accept to move forward, the investigational site will record the reason for refusing participation.

Procedures for On-site recruitment path

Subjects presenting at the Investigational Site with moderate or severe papulopustular rosacea will be informed about the possibility to participate in the trial and if they are interested the Investigator will provide further information on the study and, if the subject is interested to participate, will schedule the Screening visit at the Investigational site (V1, see below).

Common procedures for both Social Media and On-site recruitment paths

11.2.4 Screening Visit (V1, from Day -30 to Day -1)

The following procedures will be performed during the screening period:

- 1. Informed consent process and signature of the informed consent form (ICF). For subjects participating in the PK sub-study, the "PK-specific" consent signature should also be collected;
- 2. Demographics collection (age, sex, race) and health-related behaviour assessment (smoking habit, alcohol consumption, alcohol or drug abuse);
- 3. Relevant rosacea-associated medical history collection (including but not limited to family history for rosacea, age of onset etc.);
- 4. Relevant non-rosacea-associated medical history collection (attention will be paid to those medical conditions included in the exclusion criteria;
- 5. Record of previous and concomitant medications (attention will be paid to drug-associated exclusion criteria and prohibited treatments);
- 6. Vital signs recording (heart rate, blood pressure, body temperature);
- 7. Complete physical examination (including also measurement of height);
- 8. Rosacea-associated facial skin inflammatory lesion count (i.e. papules and pustules);
- 9. Five-points Investigator's Global Assessment (IGA) of Rosacea Severity;
- 10. Other rosacea-associated lesions assessment (i.e. facial erythema, facial telangiectasia, ocular manifestations, phymatous changes);
- 11. Visual analogue scale (VAS) for pain, burning/stinging and itching;
- 12. Blood collection and performance of the following laboratory tests (to be performed as close as possible to the randomisation visit [V2]):
 - haematological tests (haematocrit, haemoglobin, red blood cell count, white blood cell count with differential count, platelet count)
 - clinical chemistry tests (glycaemia, total cholesterol, triglycerides, serum creatinine, urea (or BUN), sodium, potassium, chloride, AST, ALT, Gamma-GT, alkaline phosphatase, total and fractioned bilirubin, erythrocyte sedimentation rate)
 - if not provided by the local laboratory, estimation of glomerular filtration rate
 - C-reactive protein
- 9. Urinalysis (specific gravity, pH, protein, glucose, ketones, haemoglobin, nitrite [if available], bilirubin, urobilinogen, and microscopic examination [if available]);
- 10. Serum pregnancy tests (women of child-bearing potential only);
- 11. Lactulose Breath Test (L-BT): L-BT can be performed either at the study centre under Investigator's supervision or directly by the subject at subject's home. In both cases, the test has to be performed within 14 days before the randomization visit (V2);
- 12. Check of inclusion and exclusion criteria;
- 13. Schedule Randomization visit (V2, if eligible);
- 14. Start Adverse Events collection.

11.2.5 Randomization Visit (V2, Day 1)

The following procedures will be performed at the randomization visit:

Procedures for all eligible patients:

- 1. Concomitant medications recording (change from the previous visit, attention will be paid to prohibited treatments);
- 2. Vital signs recording (heart rate, blood pressure, body temperature);
- 3. Complete physical examination (including also weight and BMI);
- 4. Urine pregnancy tests (women of child-bearing potential only);
- 5. Contraception recommendations and/or adherence (women of child-bearing potential only);
- 6. Rosacea-associated facial skin inflammatory lesion count (i.e. papules and pustules);
- 7. Five-points Investigator's Global Assessment (IGA) of Rosacea Severity;
- 8. Other rosacea-associated lesions assessment (i.e. facial erythema, facial telangiectasia, ocular manifestations, phymatous changes);
- 9. Visual analogue scale (VAS) for pain, burning/stinging and itching;
- 10. Confirmation of inclusion and exclusion criteria;
- 11. Randomization (if still eligible);
- 12. Instruct the subject on how to complete the electronic Patient Reported Outcome (ePRO), which encompasses the abdominal symptoms questionnaire (IBS-SSS) and Dermatology Life Quality Index questionnaire (DLQI).
- 13. Start of recording IBS-SSS related answers to be collected every 10 days through ePRO up to visit V4;
- 14. Start of recording DLQI related answers to be collected every 10 days through ePRO up to visit V4;
- 15. Treatment dispensing (if subject has been randomised);
- 16. Adverse Events collection.

Additional procedures for eligible patients participating also in the PK sub-study

- 17. Collection of blood samples for PK analysis;
- 18. On-site administration of the first investigational drug dose (it must be performed early in the morning after the baseline blood drawing).

11.2.6 End of Treatment Visit (V3, Day 30+1)

The following procedures will be performed at End of Treatment visit:

Procedures for all randomized patients:

- 1. Concomitant medications recording (change from the previous visit);
- 2. Vital signs recording (heart rate, blood pressure, body temperature);
- 3. Complete physical examination (including also weight and BMI);
- 4. Urine pregnancy tests (women of child-bearing potential only);
- 5. Rosacea-associated facial skin inflammatory lesion count (i.e. papules and pustules);
- 6. Five-points Investigator's Global Assessment (IGA) of Rosacea Severity;
- 7. Other rosacea-associated lesions assessment (i.e. facial erythema, facial telangiectasia, ocular manifestations, phymatous changes);

- 8. Visual analogue scale (VAS) for pain, burning/stinging and itching;
- 9. Blood collection and performance of the following laboratory tests:
 - haematological tests (haematocrit, haemoglobin, red blood cell count, white blood cell count with differential count, platelet count)
 - clinical chemistry tests (glycaemia, total cholesterol, triglycerides, serum creatinine, urea (or BUN), sodium, potassium, chloride, AST, ALT, Gamma-GT, alkaline phosphatase, total and fractioned bilirubin, erythrocyte sedimentation rate)
 - if not provided by the local laboratory, estimation of glomerular filtration rate
 - C-reactive protein
 - Urinalysis (specific gravity, pH, protein, glucose, ketones, haemoglobin, nitrite [if available], bilirubin, urobilinogen, and microscopic examination [if available]);
- 10. Check subject's recording of IBS-SSS and DLQI questionnaires via ePRO (to be ended on visit V4);
- 11. Lactulose Breath Test (L-BT): L-BT can be performed either at the study centre under Investigator's supervision or directly by the subject at subject's home. In the latter case, the test has to be performed within 3 days after the V4 visit;
- 12. Adverse Events collection;
- 13. Study drug accountability.

Additional procedures for randomized patients participating also in the PK sub-study

- 14. Collection of blood samples for PK analysis;
- 15. Administration of the last investigational drug dose (it must be performed early in the morning after the baseline blood drawing);
- 16. Overnight stay (discharge on Day 31 after the last blood drawing).

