11.2.8 Early Termination Visit (ETV, from Day 1 to Day 60)

The following procedures will be performed at the ETV visit:

- 1. Concomitant medications recording (change from the previous visit);
- 2. Vital signs recording (heart rate, blood pressure, body temperature);
- 3. Complete physical examination (including also weight and BMI);
- 4. Urine pregnancy tests (women of child-bearing potential only);
- 5. Rosacea-associated facial skin inflammatory lesion count (i.e. papules and pustules);
- 6. Five-points Investigator's Global Assessment (IGA) of Rosacea Severity;
- 7. Other rosacea-associated lesions assessment (i.e. facial erythema, facial telangiectasia, ocular manifestations, phymatous changes);
- 8. Visual analogue scale (VAS);
- 9. Blood collection and performance of the following laboratory tests:
 - haematological tests (haematocrit, haemoglobin, red blood cell count, white blood cell count with differential count, platelet count)
 - clinical chemistry tests (glycaemia, total cholesterol, triglycerides, serum creatinine, urea (or BUN), sodium, potassium, chloride, AST, ALT, Gamma-GT, alkaline phosphatase, total and fractioned bilirubin, erythrocyte sedimentation rate)
 - if not provided by the local laboratory, estimation of glomerular filtration rate
 - C-reactive protein
 - Urinalysis (specific gravity, pH, protein, glucose, ketones, haemoglobin, nitrite [if available], bilirubin, urobilinogen, and microscopic examination [if available]);
- 10. Recording of IBS-SSS and DLQI questionnaires via ePRO;
- 11. Lactulose Breath Test (L-BT): L-BT can be performed either at the study centre under Investigator's supervision or directly by the subject at subject's home. In the latter case, the test has to be performed within 3 days after the ETV visit;
- 12. Adverse Events collection.

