Blood handling and processing	Draw about 6 mL blood into the tube (the first 0.5 mL of blood withdrawn via cannula will be discarded), invert tube gently to mix and place immediately in ice/water bath. Centrifuge at 4°C at 1500 g for 10 min within 1h from collection.
Plasma aliquot volumes	Aliquot plasma evenly into two (2) polypropylene cryovial tubes. One aliquot should be retained at the site.
Plasma storage conditions	Store at below -65°C until transfer and ship on dry ice.

Samples will be analyzed within 185 days from the date of collection.

Urinalysis

Urinalysis (visual examination (specific gravity, pH, protein, glucose, ketones, haemoglobin, nitrite [if available], bilirubin, urobilinogen, microscopic examination [if available]) will be performed at the screening visit (V1), at the end of treatment visit (V3) and at the end of follow-up visit (V4) to assess systemic tolerability.

Urine pregnancy test will be performed on the sample of urines collected at V2, V3 and V4.

Lactulose breath test

Lactulose Breath Test (L-BT) is a non-invasive test for assessing malabsorption/fermentation of carbohydrates in the small intestine as consequence of SIBO. Overgrowth of colonic bacteria results in increased carbohydrate fermentation in the gut, leading to a production of hydrogen (H_2) and methane (CH₄), eventually released with the expiratory breath. Breath testing consists of times and standardised measurement of exhaled H_2 and CH₄ after the ingestion of a solution of water and lactulose. Although classical L-BT has been performed using a 4-hour collection time (Gasbarrini et

Alfasigma S.p.A.

Study code: RE-ROS2002-2021

al. 2009), a recent consensus suggests that a 2-hour procedure is sufficient to detect a significant small intestine colonization (Rezaie et al. 2017).

During the screening period (V1), L-BT will be performed to all subject recruited for participating to the clinical study within the last 2-weeks before randomization (V2). Lactulose breath test will be also repeated at the end of treatment (V3) or at the Early Termination Visit (if applicable) within 3 days from the Visit.

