5.1 Presentation

Individual patient data obtained from electronic case report forms (eCRFs), central laboratories, local laboratories, external sources, and derived data will be presented in data listings by patient. All data listings that contain an evaluation date will contain a relative study day.

All outputs will be incorporated into Microsoft Word rich text format (.rtf) files, sorted and labeled according to ICH recommendations, and formatted to the appropriate page size(s).

Tabulations will be produced for appropriate demographic, baseline, efficacy, safety, rifaximin plasma concentrations and pharmacokinetic parameters. Tabulations will be organized by using column for each treatment group, and rows for each parameter and visit (or time) where appropriate.

For categorical variables, summary tabulations of the number and percentage of patients within each category (with an "unknown" category for missing data) of the parameter will be presented. Denominators for percentage calculations will include missing data, unless otherwise specified in the table description. Percentages are rounded to 1 decimal place, unless otherwise specified in the table shell.

For continuous variables, the number of patients, mean (arithmetic), SD, median, interquartile range (IQR), minimum, and maximum values will be presented. The precision of summary statistics, unless otherwise specified, will be as follows: mean, median, and IQR to 1 more decimal place than the raw

data and SD to 2 decimal places more than the raw data. In general, the decimal places should not exceed 3 decimal places unless appropriate. Cls will be provided and will be rounded to 1 more decimal place than the raw data, unless otherwise specified in the table and listing shell.

For ordinal variables, the summary procedures for both categorical and continuous variables will be followed where appropriate.

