5.8 Visit Windows

No visit windows will be applied for this study.

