With reference to efficacy analyses performed on the FAS, the last observation carried forward (LOCF) strategy will be employed for dealing with any missing continuous post-baseline data for the relevant primary and secondary endpoints. For binary data (i.e. Success/Failure) missing data will be considered as Failures, unless differently specified in the appropriate analysis section for that data.

With reference to other categorical variables, the number of patients with missing data will be presented under the "unknown" category. Missing values will be included in the denominator count when computing percentages, unless differently specified in the appropriate analysis section for that data.

LOCF imputation will be used for the inferential analysis of categorical variables.

When other continuous data will be summarized, only the non-missing values will be evaluated for computing summary statistics.

Missing data in safety variables will not be imputed/replaced unless otherwise specified in the analysis section.

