5.13 Dry Run

Blinded dry-run(s) will occur prior to final database lock and unblinding in order to allow a review of clinical trial data and tables, listings, and figures. Consequences on the statistical analysis will be discussed and documented.

6 Summary of Study Data

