6.3 Protocol Deviations

Protocol deviations for lack of compliance, mis-stratification, inadequate or missing informed consent, intake of study treatment other than the one assigned, incorrect doses and prohibited treatments, missed visits, missed assessments, out-of-window visits or assessments, and violations of inclusion/exclusion criteria (where possible) will be determined based on available data. All other protocol deviations will be collected by the clinical research associates.

Protocol deviations that could potentially affect the efficacy or safety conclusions of the study will be identified, and the assessment of determination of evaluable patients for analysis populations (FAS, mFAS, SAF, PP and PK) will be performed and approved by the Study Statistician, Medical Monitor, and Clinical Study Manager prior to database lock and unblinding of individual patient treatment information.

The process applied for the identification of protocol deviations will be described in a specific document.

All protocol deviations will be listed and summarized by treatment group. To identify deviation categories and sub-categories for summarization, the "Sponsor PD Number" variable in the excel workbook containing the list of protocol deviations will be used. The main category will be identified by the first number and the sub-category will be identified by the second number. As an example: if a code is "1.3", "1" is the main category code and "3" is the sub-category code.

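### Protocol 11.2.6 times the home end-of-treatment breath test from V4 (Day 60), in conflict with Protocol 11.3, both schedules and the V4 list (minor internal inconsistency)

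*Protocol*

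**What the plan says.** Protocol 11.2.6 lists the V3 procedures. Item 11 allows the L-BT at the centre or at the patient's home, and for the home test adds: "In the latter case, the test has to be performed within 3 days after the V4 visit".

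The other places that time this test read differently:

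- Protocol 11.3: "Lactulose breath test will be also repeated at the end of treatment (V3) or at the Early Termination Visit (if applicable) within 3 days from" whichever of those two applies.
- Protocol 11.1 and SAP Table 3 (schedules): L-BT is marked at V1, V3 and the early termination visit (ETV), and at an unscheduled visit if judged necessary. The V4 cell is blank.
- Protocol 11.2.7 (V4 list): 13 items, none of them an L-BT. The last item closes the study for the patient.
- Protocol 11.2.8, item 11 (ETV): "In the latter case, the test has to be performed within 3 days after the ETV visit". This governs another visit and counts from that visit.

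On analysis, SAP 8.4 summarises L-BT status and numerical H2 and CH4 results, covers screening and end of treatment, and adds shift tables. Protocol 16.3.5 tabulates L-BT by treatment group, stratification factor and visit. SAP 5.8 states: "No visit windows will be applied for this study".

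**The concern.** Item 11 is a mandatory instruction to sites, and it attaches a Day 30 assessment to a visit about a month later. Within one item, the same assessment would fall at about Day 30 if done in clinic and about Day 60 if done at home. The literal home test would also come at or after the visit that ends the patient's study.

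For a patient who completes treatment, V3 is the only scheduled L-BT after screening. If some home tests were done around V4, the end-of-treatment row and the shift tables in SAP 8.4 could present two time points as one, or could lose those patients. In addition, while two timing rules stand in the protocol, it is unclear which home tests count as out of window.

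**Working it through.** There is no plan figure to reproduce. The check is a comparison of passages plus day-window arithmetic.

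**Inputs**

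- V3 = Day 30±1, so Day 29–31 (Protocol 11.1, 11.2.6).
- V4 = Day 60±3, so Day 57–63 (Protocol 11.1, 11.2.7).
- Home margin = 0 to 3 days after the reference visit (Protocol 11.2.6 and 11.2.8, item 11 of each).
- Nominal last dose = Day 30 (Protocol 10.1).

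**Windows**

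1. Clinic test on the day of V3: Day 29–31.
2. Home test, item 11 read literally: 57 + 0 = 57 to 63 + 3 = 66, so Day 57–66.
3. Home test timed from V3: 29 + 0 = 29 to 31 + 3 = 34, so Day 29–34.
4. Smallest separation between windows 2 and 3: 57 − 34 = 23 days. They do not overlap.
5. Literal home test after the patient's own V3: 57 − 31 = 26 to 66 − 29 = 37 days. With both visits on their nominal days: 60 − 30 = 30 to 63 − 30 = 33 days.
6. Literal home test after the nominal last dose: 57 − 30 = 27 to 66 − 30 = 36 days. Timed from V3: 29 − 30 = −1 to 34 − 30 = 4 days.

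The three-day margin in Protocol 11.3 is not limited to home tests. A clinic test could therefore also run to Day 34, and the literal home window still starts 23 days later.

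**What happens to a literal home result**

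- Filed under V3: with no visit windows (SAP 5.8), it enters SAP 8.4 as end of treatment whatever its date.
- Filed under V4: it drops out of SAP 8.4, which reports screening and end of treatment only. Protocol 16.3.5, by visit, could still show it.

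**Where L-BT enters inference**

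Randomisation strata (SAP 4.3), the ANCOVA and CMH analyses (SAP 7.1, 7.2) and the L-BT, H2 and CH4 subgroups (SAP 5.7) all rest on the screening test. The post-treatment result enters none of them.

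**Early termination tests**

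The ETV can fall anywhere from Day 1 to Day 60. Neither document says whether its L-BT counts as end of treatment. The sample size section expects about 10% dropout: 0.10 × 201 ≈ 20 patients. If their ETV tests are placed in the end-of-treatment row, that row mixes time points even when the protocol is followed correctly.

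**The case against.** The strongest reply is that this is an evident slip. Item 11 sits under a Day 30 heading, and 11.3, both schedules and the V4 list all agree against it. The SAP also has tools to catch a late test:

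- SAP 6.3 identifies "missed assessments, out-of-window visits or assessments" as deviations.
- SAP 5.1 states: "All data listings that contain an evaluation date will contain a relative study day".
- SAP 5.13 states: "Blinded dry-run(s) will occur prior to final database lock and unblinding".

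Most of this stands, and it is why the point is minor. It does not remove the point. The tools can reveal a late test, but no stated rule says what to do with it, and 6.3 cannot classify it while two windows coexist.

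Four stronger readings are tempting and are not supported:

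- **A deliberate Day 60 test.** The background describes an open-label study that repeated its breath test a month after therapy, so Day 60 may look intended. But item 11 itself places the clinic test at V3, and the V4 list has no L-BT.
- **A contradiction with the ETV item.** That item is a parallel for another visit. It shows the intended pattern of counting from the visit's own date and does not contradict item 11.
- **Mixed data or biased efficacy results.** Mixing needs a site to follow item 11 literally and the result to be filed under V3. Neither can be checked here, because the eCRF, laboratory manual and table shells are not available. Nothing suggests a difference between arms.
- **A count of affected patients.** The share of home tests is not stated, so no number can be given. A test timed from V4 also requires the patient to reach V4, so patients who drop out earlier are not exposed.

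**Conclusion.** The textual conflict is certain: the current wording of Protocol 11.2.6 item 11 cannot be reconciled with 11.3, the two schedules and the V4 list. It is an internal inconsistency of minor severity.

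The two possible home windows, Day 29–34 and Day 57–66, are at least 23 days apart, so recorded test dates can tell them apart. The consequence is conditional and confined to the descriptive L-BT summary, the H2 and CH4 values and the shift tables. The co-primary and secondary efficacy analyses, the strata and the subgroups are not touched. The windows assume that visits fall within their stated ranges and that the last dose is on Day 30.

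**What to change.** - **Protocol:** reconcile 11.2.6 item 11 with 11.3 and both schedules, so that the home test is timed from the visit it belongs to (V3). Use the same preposition throughout: item 11 and the ETV item say after, while 11.3 says from, which may admit a test shortly before the visit. Tell sites if any are still active.
- **SAP 8.4:** define the end-of-treatment L-BT by test date relative to V3. State explicitly how ETV tests are handled, for example included under a stated rule or shown in a separate row.
- **Before lock:** check recorded L-BT dates at the blinded dry run and list tests done around V4 separately.

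The cost is a small wording change in the protocol, a site memo if still useful, a short addition to the SAP and one date check. The downside is that patients tested around V4 would have no end-of-treatment L-BT value. L-BT sits in the safety section of the SAP, and SAP 5.9 says: "Missing data in safety variables will not be imputed/replaced unless otherwise specified in the analysis section". If the final rule excludes tests before V3, a home test done shortly before that visit would be lost in the same way. Listing such tests keeps them visible.
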